- 19. Subjects' self-monitoring of blood glucose: the subjects should be monitored for the fasting or postprandial fingertip blood glucose at home as required, and measured as required during the introduction period. The recommended test frequency during the double-blind treatment phase is 1-2 times a week. Additional blood glucose measurement is required when symptoms of hypoglycemia or hyperglycemia are suspected and recorded in the subject diary. At each visit, the investigator needs to carefully review the subject diary, and provide suggestions for the subject's following blood glucose monitoring according to the records in the subject diary. For detailed procedures, please refer to APPENDIX 10.
- 20. Dosing regimen: during the introduction period, all subjects are given the placebo, and are administered with the corresponding investigational drug according to the grouping of subjects after randomization. Salvage therapy is to use the salvage drug in addition to the investigational drug.
- 21. Distribution of the salvage therapy drug: it is only applicable when the salvage therapy is successful, and will be distributed together with the investigational drug in the follow-up routine visits during the double-blind treatment phase.

*The local laboratory is responsible for testing and feedback of measurements.

**The central laboratory is responsible for unified testing.

TABLE OF CONTENTS

Pı	rotoc	ol Synops	sis	1
St	udy _l	process		9
Ta	able o	of Conten	ts	17
Li	ist of	abbrevia	tions	22
G	lossa	ry		23
1.	S	TUDY B	ACKGROUND	24
	1.1	Diseas	e Introduction	24
	1.2	Drug I	ntroduction	25
		1.2.1	Drug name and physicochemical characterization	25
		1.2.2	Mechanism of action	25
		1.2.3	Non-clinical studies	27
		1.2.4	Clinical study	30
	1.3	Justific	cation for Study Design	31
	1.4	Risk B	Benefit Assessment	32
2.	S	TUDY O	BJECTIVES	34
	2.1	Primai	ry Objective	34
	2.2	Second	dary Objectives	34
3.	S	UBJECT	SELECTION AND WITHDRAWAL	35
	3.1	Inclusi	ion Criteria	35
	3.2	Exclus	sion Criteria	35
	3.3	Withd	rawal Criteria	38
		3.3.1	Principles for withdrawal due to hypoglycemia	39
		3.3.2	Principles for withdrawal due to failure in hyperglycemia salv therapy	_
	3.4	Early	Termination of Study/Closure of Study Site	42
	3.5	Defini	tion of End of Study	42
4.	S	TUDY D	ESIGN	43
	4.1	Study	Type and Design Principles	43
	4.2	Rando	mization and Blinding	44
		4.2.1	Randomization method	44
		4.2.2	Blinding and blind execution	44
		4.2.3	Emergency unblinding principle	45

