	Visit	V1 ¹	V2	V3	V4 ¹	V5	V6	V7/Withdr awal Visit	V8	Not applicable	Not applicable
Weeks (Days)		Week -6 to Week -4	Week -4	Week -1 (Day -7 to Day -5)	Day1	Week 4 (Day 28)	Week 8 (Day 56)	Week 12 (Day 84)	Week 16 (Day 112)	Not applicable	Over 4 weeks of salvage therapy
Visit Window		Not applicab le	Not applicabl e	Not applicable	Not applicabl e	±3 days	±3 days	±3 days	±3 days	Not applicable	±3 days
Radiograp	12-lead ECG ¹⁸	X*		X*	X*	X*	X*	X*		X*	X*
hy and Auxiliary Examinations	Liver Transient Elastography (including LSM and CAP)	X*		X*				X*		X*	
	Abdominal Color Doppler Ultrasound (kidneys, liver, gallbladder, pancreas, spleen)			X*							
Treatment	Guidance on Lifestyle	X	X	X	X	X	X	X		X	X
	Self-monitoring of Blood Glucose 19					X					
	Guidance on Investigational Drug		X	X	X	X	X				
	Distribution of Investigational Drug		X		X	X	X				

Nomenclature HTD1801/Clinical Phase II Protocol No.: HTD1801.PCT103

	Screenin g Phase		e-blind tion Period	Double-blind Treatment Phase				Safety Follow-up Visit Phase	Pre- salvage Therapy Visit ⁴	Salvage Therapy Evaluation Visit ⁵
Visit	V1 ¹	V2	V3	V4 ¹	V5	V6	V7/Withdr awal Visit	V8	Not applicable	Not applicable
Weeks (Days)	Week -6 to Week -4	Week -4	Week -1 (Day -7 to Day -5)	Day1	Week 4 (Day 28)	Week 8 (Day 56)	Week 12 (Day 84)	Week 16 (Day 112)	Not applicable	Over 4 weeks of salvage therapy
Visit Window	Not applicab le	Not applicabl e	Not applicable	Not applicabl e	±3 days	±3 days	±3 days	±3 days	Not applicable	±3 days
Dosing Regimen 20			X	X						
Recovery of Investigational Drug			X	X	X	X	X			
Distribution of Salvage Therapy Drug ²¹									X	X ²¹
Distribution of Subject Diary		X		X	X	X				
Recovery of Subject Diary			X	X	X	X	X			
Compliance Assessment			X	X	X	X	X			
Recording of Concomitant Medications or Non-drug Therapy		X	X	Х	Х	X	X	X	X	Х
Recording of AEs	X	X	X	X	X	X	X	X	X	X

Note:

1. If V1 and V2 are on the same day, the two visits can be pooled into one visit. The laboratory test, 12-lead ECG, and fasting plasma glucose (FPG) test results within 1 week prior to screening (including before signing the ICFs) in this study site are accepted (if plasma glucose cannot be tested, serum glucose results are acceptable); HbA1c test results within 4 weeks prior to screening in this study site are accepted. The test indicators on the day of randomization (V4) are not used as the basis for the inclusion/exclusion review.

Protocol No.: HTD1801.PCT103

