- 2. Withdrawal visit: only for subjects who have received investigational drug and withdraw the study treatment after randomization. For subjects who withdraw their ICFs, the subjects are recommended to return to the study site for a withdrawal visit within 1 week after confirmed withdrawal. The withdrawal visit procedure is the same as that of V7. If the subject withdraws early during the safety follow-up visit, the visit procedure should be the same as that of the safety follow-up visit (V8).
- 3. Safety follow-up visit (V8) is conducted by telephone visit to inquire about the occurrence of AEs and concomitant medication. If the subject should be re-tested according to the investigator's judgment on the laboratory results of the subject at Week 12, then the subject should be arranged to come to the study site for follow-up visit. For subjects who failed in the randomization and who did not receive the investigational drug after randomization, no 4-week post-dose safety follow-up visit is required. During the safety follow-up visit, the investigator can give the subjects other anti-diabetic drug treatment (without berberine and ursodeoxycholic acid) according to the subject's condition and diagnosis and treatment guidelines for diabetes mellitus.
- 4. Pre-salvage therapy visit: investigators should retest the fasting plasma glucose of the subject in the central laboratory within 7 days after being informed that the subject's test result has reached the hyperglycemia threshold for salvage therapy. Subjects whose central laboratory re-test results meet the hyperglycemia threshold for salvage therapy will receive the pre-salvage therapy visit before the salvage therapy. If the time point between the pre-salvage therapy visit and the follow-up routine visit (V5 or V6) in the double-blind treatment phase is ≤7 days, the next treatment visit (V5 or V6) is not required. If the subject has contraindications to salvage therapy, the pre-salvage therapy visit is not required, and the subject should withdraw from the study early and receive the withdrawal visit.

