- 5. Salvage therapy evaluation visit: if the subject has received salvage therapy for 4 weeks during the 12-week double-blind treatment phase, a salvage therapy evaluation visit is required to evaluate the effect of salvage therapy by FPG; if the salvage therapy evaluation visit time (including the visit window) coincides with the routine visit time (including the visit window) during the double-blind treatment phase, they will be pooled into one visit, and the content of the visit should meet the requirements of both visits; the effect of salvage therapy will be evaluated according to FPG. If the subject's FPG does not reach the corresponding hyperglycemia threshold set in the protocol, it is defined as success in salvage therapy, and the subject will continue to use salvage therapy drugs in addition to the investigational drug according to the protocol. If the subject's FPG reaches the corresponding hyperglycemia threshold set in the protocol, it is defined as failure in salvage therapy, and the subject will withdraw from the study and receive a withdrawal visit. If the subject is receiving salvage therapy at the end of the 12-week double-blind treatment phase, but the salvage therapy duration was less than 4 weeks, the salvage therapy evaluation visit is not required, and the V7 visit is carried out according to the normal procedure.
- 6. Demographic data: information such as gender, age, ethnicity and/or date of birth, etc.
- 7. Physical examinations: skin, mucous membranes, lymph nodes, head, neck, chest, abdomen, spine/limbs.

8. Vital signs: pulse, temperature, sitting blood pressure (systolic and diastolic) measurement. Subjects should be measured at rest. It is recommended that blood pressure be measured on the same arm for each subject at each visit throughout the study.

Protocol No.: HTD1801.PCT103

- 9. Etiological test: including hepatitis B virus surface antigen (HBsAg), hepatitis B virus (HBV-DNA) test (if necessary), hepatitis C virus antibody (HCV-Ab), hepatitis C virus (HCV-RNA) test (if necessary), treponema pallidum antibody (TP-Ab), human immunodeficiency virus antibody (HIV-Ab).

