- 10. Pregnancy test: for female subjects of childbearing age only (see APPENDIX 6). The blood pregnancy test is required at V1, V3, and V7 in the local laboratory. During the study V5 and V6, a urine pregnancy test should be performed in local laboratories, and if the urine pregnancy test is positive, a blood pregnancy test should be performed immediately to exclude or verify the pregnancy. If the blood pregnancy test at V1 is positive, the subject will not be able to participate in the study. Female subjects should withdraw from the study immediately once the blood pregnancy test is positive.
- 11. Thyroid function tests: free tri-iodothyronine (FT3), free thyroxine (FT4) and thyroid stimulating hormone (TSH).
- 12. Evaluation endpoints: for the sample collection time window, see APPENDIX 8.
- 13. Except for the blood samples collected after meals, other blood samples should be collected under the fasting condition (V1, V3, V4-7, withdrawal visit, pre-salvage therapy visit, and salvage therapy evaluation visit). It is recommended to collect the fasting blood samples at 7:00 ~ 10:00 a.m.
- 14. After meals: standard meals are given. For detailed procedures, please refer to APPENDIX 9. For the time window, please refer to the APPENDIX 8.
- 15. Liver function and blood lipid test: for LDL-C, HDL-C, TG, TC, AST, ALT, GGT, TBIL, the time windows are shown in APPENDIX 8.
- 16. Feces collection (if any): feces samples of subjects should be collected from the day before the visit to the day of the visit according to the subject's own conditions if possible. Refer to the *Laboratory Operation Manual* for the relevant procedures of feces collection. A lifestyle background survey can be conducted at the same time as the baseline feces collection to better guide the subject's lifestyle.
- 17. PPK blood sample collection: V4 blood samples should be collected under the fasting condition in the forenoon, V5-V7 blood samples should be collected before breakfast on the same day (before the first administration) (time window: within 1 hour before dosing).
- 18. 12-lead ECG: subjects should be checked in the supine position after rest, and the heart rate, PR interval, QT interval, RR interval, QTcF (see APPENDIX 5 for calculation formula) and QRS complex duration should be recorded.

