4.3.9 Pre-salvage therapy visit

Investigators should give the subjects the central laboratory test again for FPG within 7 days of being informed that the subject's test results have reached the hyperglycemia threshold for salvage therapy (see Section 3.3.2). Subjects whose central laboratory test results meet the hyperglycemia threshold for salvage therapy will receive the pre-salvage therapy visit before the salvage therapy. If the time point between the pre-salvage therapy visits and the follow-up routine visit (V5 or V6) in the double-blind treatment phase is ≤ 7 days, the follow-up routine treatment visit (V5 or V6)

is not required. If the subject has contraindications to salvage therapy, the pre-salvage therapy visit is not required, and the subject should withdraw from the study early and receive the withdrawal visit.

Protocol No.: HTD1801.PCT103

The subject should arrive at the study site under the fasting condition. The blood samples should be collected under the fasting condition. It is recommended to collect the fasting blood samples at $7:00 \sim 10:00$ a.m. Procedures to be completed at this visit include:

- Body weight;
- Clinical laboratory tests (blood biochemistry, hematology, urinalysis; the specific items included are shown in APPENDIX 7);
- PPK blood sample collection (within 1 hour before dosing);
- HbA1c;
- Fasting blood glucose, fasting insulin, fasting C-peptide;
- Liver function and blood lipid test (LDL-C, HDL-C, TG, TC, AST, ALT, GGT, TBIL, fasting);
- C-reactive protein (fasting);
- Intestinal flora metabolomics serum samples (fasting);
- 12-lead ECG;
- Liver transient elastography;
- Feces collection (if any);
- Guidance on lifestyle;
- Distributing the drug for salvage therapy;
- Recording concomitant medications or treatments;
- Recording AEs.

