5.1.3.3 Salvage therapy

If the subject meets the criteria for initiating the salvage therapy (see Section 3.3.2.1), the salvage therapy should be initiated with Empagliflozin. On the basis of treatment with the investigational drug, the investigator will determine the usage and dosage of Empagliflozin according to the conditions of the subjects, and referring to the instructions for use of Empagliflozin and Diagnosis and Treatment Guidelines for Diabetes Mellitus.

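### A pre-salvage visit can replace V5 or V6, but it omits study-drug dispensing, vital signs, physical examination, the urine pregnancy test and, for V6, the standard meal

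*Protocol*

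**What the plan says.** Note 4 of the Study process table sets a waiver: if 7 days or fewer separate the pre-salvage visit from the routine visit that follows it, "the next treatment visit (V5 or V6) is not required". Section 4.3.9 repeats the rule in the body text.

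The content of the pre-salvage visit is fixed in two places that agree, the procedure list in Section 4.3.9 and the visit's column in the Study process table. The only product handed out is the rescue drug: "Distributing the drug for salvage therapy". In the row "Distribution of Investigational Drug", the treatment-phase marks are at V4, V5 and V6 only.

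Study drug does not stop at rescue. Note 20 says: "Salvage therapy is to use the salvage drug in addition to the investigational drug". Section 5.1.3.3 opens its dosing rule with "On the basis of treatment with the investigational drug". On pregnancy testing, note 10 says: "During the study V5 and V6, a urine pregnancy test should be performed in local laboratories".

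Note 5 covers the related case in which the salvage evaluation visit coincides with a routine visit. There the two are pooled and "the content of the visit should meet the requirements of both visits". Note 4 has no such clause.

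**The concern.** A visit that stands in for another should carry over what the other was there to do, or the protocol should say where those items go. Here one visit is removed and its replacement has a narrower list. Nothing in the protocol moves the missing items to the pre-salvage visit.

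Three things are at stake for a subject who meets the waiver:

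- **Treatment continuity.** The subject must keep taking study drug, but the scheduled occasion for receiving it has gone.
- **Safety checks.** Vital signs, physical examination and, for women of childbearing age, the pregnancy test are put off just as a second drug is started.
- **Week 8 data.** If V6 is the waived visit, the standard meal is not done, so the Week 8 values of three secondary endpoints in Section 7.2 (postprandial glucose, insulin and C-peptide) are not collected.

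**Working it through.** The plan gives no figure to reproduce. The check is an item-by-item comparison of the visit lists, followed by day arithmetic on the scheduled visits.

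**Visit content** (Sections 4.3.5, 4.3.6, 4.3.9 and 4.3.10, checked against the Study process table):

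| Item | V5 | V6 | Pre-salvage | Salvage evaluation |
|---|---|---|---|---|
| Study-drug dispensing | yes | yes | **no** | no |
| Vital signs | yes | yes | **no** | yes |
| Physical examination | yes | yes | **no** | yes |
| Urine pregnancy test | yes | yes | **no** | no |
| Standard meal, 0.5-hour samples | no | yes | **no** | no |
| HbA1c | no | yes | yes | no |
| Fasting insulin and C-peptide | yes | yes | yes | no |
| Fasting glucose | yes | yes | yes | yes |
| Biochemistry, hematology, urinalysis | yes | yes | yes | yes |
| ECG | yes | yes | yes | yes |

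The pre-salvage visit therefore covers most of the blood work. The gap is the five items in bold. The list also omits drug return, diary exchange and the compliance assessment, but Sections 5.3, 5.4 and 6.2 largely recover these later, so they are not counted here.

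**Scheduled days:** V3 is Day -7 to Day -5, V4 is Day 1, V5 is Day 28, V6 is Day 56 and V7 is Day 84. Visit windows and the absence of a Day 0 are ignored below.

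**Interval between scheduled study-drug dispensings**
- V5 waived: V4 to V6 = 56 - 1 = 55 days, instead of 28 - 1 = 27.
- V6 waived: the last dispensing is V5. V7 dispenses none, so that supply has to serve 84 - 28 = 56 days, instead of 56 - 28 = 28.

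These are intervals on the schedule, not days without drug.

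**Interval between pregnancy tests**
- V5 waived: V3 to V6 = 56 + 5 to 56 + 7 = 61 to 63 days, about 9 weeks. With V5 held it is 28 + 5 to 28 + 7 = 33 to 35 days, about 5 weeks.
- V6 waived: V5 to V7 = 84 - 28 = 56 days, 8 weeks. With V6 held it is 28 days, 4 weeks.

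**Interval between scheduled vital signs**, assuming salvage starts on the day of the pre-salvage visit, so that the evaluation visit comes 28 days later
- V5 waived: pre-salvage on Day 21 to 28, evaluation on Day 49 to 56. From Day 1 this is 48 to 55 days, instead of 27.
- V6 waived: pre-salvage on Day 49 to 56, evaluation on Day 77 to 84. From Day 28 this is 49 to 56 days, instead of 28.

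**The case against.** The waiver looks deliberate, and the substitute visit is substantial. It has the fasting efficacy samples, safety laboratory tests, ECG (which records heart rate) and body weight, and it adds HbA1c, C-reactive protein and elastography, which V5 lacks. The wording makes V5 or V6 optional, so a site may still hold it. Unscheduled visits are allowed (Section 4.3.11), extra tests are allowed (Section 7.3.4), and Section 5.3 obliges investigators to see that study drug is taken properly. Physical examination and vital signs return at the salvage evaluation visit. Contraception is a condition of entry, and a blood pregnancy test remains at V7. A missing interim postprandial value is something the repeated-measures model in Section 10.4 can accommodate.

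The number of subjects is also likely to be small. Scheduled central-laboratory fasting glucose is taken at the routine visits, so a rescue triggered by V5 would tend to fall soon after V5, not in the week before V6. Before V5 the threshold is 15.0 mmol/L, while entry required less than 13.9 mmol/L. In the other direction, the threshold drops to 13.3 mmol/L from Week 7, which could bring some pre-salvage visits into the week before V6. Neither effect can be quantified from the protocol.

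Most of this stands, and it limits the size of the point. It does not remove it. The permissive routes let a site repair the gap but do not tell it to. Section 5.3 also requires dispensing to follow the protocol, which schedules none at this visit. Section 4.3.11 ties efficacy assessments to the planned visits, so it does not clearly restore the Week 8 meal.

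A reader might infer that rescued subjects will run out of study drug. The protocol does not support that: it does not state the quantity dispensed per visit, and one supply with enough overage could span two intervals.

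**Conclusion.** The point holds as a minor defect in a stated rule. Read literally, note 4 and Section 4.3.9 remove a visit and do not carry over five of its requirements, although study drug must continue and note 5 already handles the related case correctly.

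For a subject who meets the waiver, no study drug is scheduled until the next routine visit (none at all if V6 is waived). The interval between pregnancy tests is about 8 to 9 weeks for women of childbearing age, and vital signs are about 7 to 8 weeks apart. If V6 is waived, the Week 8 postprandial values are lost. The vital-signs figure assumes that salvage starts at the pre-salvage visit. The other intervals follow from the scheduled days alone.

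The protocol gives no rescue rate, so the number of affected subjects cannot be calculated. A 7-day interval before each of two visits suggests few. It would also be wrong to infer harm to the primary analysis: HbA1c at Week 12 is still measured at V7, the pre-salvage visit itself includes HbA1c, and the Week 12 postprandial values remain.

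**What to change.** Add to note 4 and Section 4.3.9 that a pre-salvage visit replacing V5 or V6 must meet the requirements of both visits, as note 5 already says for the salvage evaluation visit. Spell out two consequences:

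- **Study drug.** Dispense enough to reach the next dispensing visit, or V7 if V6 is replaced, including the +3-day window. From a visit held 7 days early this is up to 28 + 7 + 3 = 38 days of dosing, less any usable supply the subject keeps.
- **Standard meal.** If V6 is replaced, do the meal and its 0.5-hour samples before the first dose of salvage drug, and record the actual study day. Holding the meal later at a retained V6 would measure the response after empagliflozin has started, which is a different quantity. The protocol should therefore name one option, and the meal before salvage is preferable.

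The cost is two or three sentences and a slightly longer visit for a few subjects, using only procedures that V5 and V6 already contain. The Week 8 meal test would be up to 7 days early for a subject whose V6 is replaced, which the recorded study day makes visible.

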TREATMENT (GUIDELINES FOR THE PREVENTION AND TREATMENT OF		96
1 YPE 2 DIABETES MELLITUS IN CHINA (2020))98	TYPE 2 DIABETES MELLITUS IN CHINA (2020))	98

LIST OF ABBREVIATIONS

Protocol No.: HTD1801.PCT103

Abbreviation	Full Name in English
AE	Adverse event
ALP	Alkaline phosphatase
ALT	Alanine aminotransferase
AST	Aspartate aminotransferase
AUC _{0-t}	Area under the curve from pre-dose to the time of the last observation
BBR	Berberine
-	
BBR·Cl	Berberine hydrochloride
BID	Twice a day
BMI	Body mass index
CAP	Controlled attenuation parameter
CDE	Center for drug evaluation, national medical products administration
C _{max}	Maximum plasma concentration
CRO	Contract research organization
CTCAE	Common terminology criteria for adverse events
CYP450	Cytochrome P450
DBIL	Direct bilirubin
DPP-4	Dipeptidyl peptidase IV
eCRF	Electronic case report form
eGFR	Estimated glomerular filtration rate
EDC	Electronic data capture
FAS	Full analysis set
FDA	Food and drug administration
FPG	Fasting plasma glucose
FXR	Farnesoid X receptor
G6PD	Glucose-6-phosphate dehydrogenase
GCP	Good clinical practice
GGT	Gamma-Glutamyl Transferase
GLP-1	Glucagon-like peptide-1
HbA1c	Glycosylated hemoglobin
HBsAg	Hepatitis B virus surface antigen
HCV-Ab	Hepatitis C virus antibody
HDL-C	High-density lipoprotein cholesterol
HED	Human equivalent dose
HIV-Ab	Human immunodeficiency virus antibody
IC ₅₀	50% inhibitory concentration
ICF	Informed consent form
ICH	International council for harmonisation of technical requirements for
	pharmaceuticals for human use
IR	Insulin resistance
ITT	Intention-to-treat analysis
LDL-C	Low-density lipoprotein cholesterol
LLN	Lower limit of normal
LOCF	Last observation carried forward

Abbreviation	Full Name in English
LSM	Liver stiffness measurement
MedDRA	Medical dictionary for regulatory activities
MMRM	Mixed model repeated measures
MTD	Maximum tolerated dose
NASH	Nonalcoholic steatohepatitis
NOAEL	No observed adverse effect level
NYHA	New york heart association
PKS	Pharmacokinetic set
PPK	Population pharmacokinetics
PPS	Per protocol set
PSC	Primary sclerosing cholangitis
PT	Preferred terms
QA	Quality assurance
QTcF	Corrected QT interval by Fredericia's formula
SAE	Serious adverse event
SGLT2i	Sodium-glucose cotransporter-2 inhibitor
SOC	System organ class
SS	Safety set
SOP	Standard operation procedure
SUSAR	Suspected unexpected serious adverse reaction
SMBG	Self-monitoring of blood glucose
T2DM	Type 2 diabetes mellitus
TBIL	Total bilirubin
TC	Total cholesterol
TG	Triglyceride
TGR5	Takeda G protein-coupled receptor 5
TP-Ab	Treponema pallidum antibody
TSH	Thyroid stimulating hormone
UDCA	Ursodeoxycholic acid
ULN	Upper limit of normal
UGT	UDP-glucuronosyltransferase
WHO	World health organization
WHO DD	World health organization drug dictionary

GLOSSARY

Investigational Drug	HTD1801
Control Drug	Placebo
Study Products	Invstigational drug and control drug
Drug for Salvage Therapy	Empagliflozin

